- Other Treatment-related adverse events requiring surgical intervention prior to Week 12 post-treatment and all serious adverse event (SAE) occurrences throughout the study.

We predict non-inferiority in safety measures between ReCell-treated areas and control

areas of the wound.

Specific Aim 2: Evaluate the **preliminary effectiveness** of ReCell treatment of full-thickness wounds treated with STSG over INTEGRA™ MBWM compared to a control site. Preliminary effectiveness will be assessed during an acute healing phase (Week 1–6) and will focus on healing of both wound and donor sites. Evaluations to be performed include:

- Wound epithelialization
- Histology
- Patient pain rating

We predict that, at each time point, more ReCell-treated areas will be healed to an extent defined as non-inferior compared to the control areas of the wound.

Specific Aim 3: Evaluate the **long-term effectiveness** of ReCell treatment of full-thickness wounds treated with INTEGRA™ MBWM compared to a control site. Long-term effectiveness will be assessed at Weeks 12 and 24 post-ReCell treatment. Evaluations will focus on the integrity and durability of regenerated tissue as well as physical characteristics such as pliability and cosmesis. Patient satisfaction will also be evaluated. Evaluations to be performed include:

- Scar assessment scale using the Patient and Observer Scar Assessment Scale (POSAS) and Vancouver Scar Scale
- Functional outcome rating
- Patient satisfaction
- Histology
- Radiographic evaluation for assessment of heterotopic ossification

We predict that scar/functional outcomes and patient satisfaction metrics will be non-inferior for ReCell treated areas.

INTRODUCTION TO STUDY CONDUCT

This document is a protocol for a human research study. This study is to be conducted according to US and international standards of Good Clinical Practice (International Conference on Harmonization ICH E6), the Code of Federal Regulations Title 21 parts 803 and 812, and other applicable government regulations and Institutional research policies and procedures. No amendment to the protocol or deviation from the protocol will be implemented without the prior review and approval of the Institutional Review Board (IRB) except where it may be necessary to eliminate an immediate hazard to a research participant. In such a case, the deviation will be reported to the IRB as soon as possible.

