The wound area to be followed in the study will be between 200cm² and 640cm². One ReCell kit is intended to treat up to 320cm² (which will cover half of the total “maximum” 640cm² wound area), allowing for comparison with a similar size control area of up to 320cm² that is treated according to the standard of care.

In all cases, the ReCell region may be up to 320cm² in size, the upper limit of application area for one ReCell kit, with a similarly sized control region. If the wound is larger than the combined control and ReCell regions (over 640 cm²), areas outside the study regions will be designated non-study areas and treated according to the standard of care. Additionally, areas with incomplete granulation, defined as a contiguous vascularized granulation layer at the INTEGRA™ MBWM application site, will be excluded from the study wound area.

The same primary and secondary dressings will be used on ReCell-treated areas, control areas and donor sites. Once the wounds are determined to be healed, standard local clinical practice will be followed.

In order to evaluate improvements associated with use of ReCell, within-subject comparisons across a battery of measurements and evaluations will be made. These measurements are divided into three categories:

- Safety and tolerability measures
- Preliminary effectiveness (acute healing phase)
- Long-term effectiveness

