5.7.2 Sample Size Estimation

No formal sample size estimation has been performed since this is a feasibility study. A sample size of 20 subjects was selected based upon the amount of subject exposure considered necessary in order for clinical assessments of safety, tolerability, preliminary and long-term effectiveness of the ReCell device when used for healing of full-thickness wounds treated with 1:5 meshed STSG and INTEGRA MBWM. This study does not evaluate formal hypotheses and is not prospectively powered to detect potentially clinically significant improvements in study endpoints. The results of this feasibility study may be analyzed to refine the study design for a pivotal trial.

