5.7.3 Data and Statistical Analysis Plan

Due to the feasibility nature of this clinical trial, no formal statistical analysis nor interim analysis will be performed. Data collected in this study will be documented using summary tables. Quantitative variables will be summarized using descriptive statistics, including mean (and/or median), standard deviation (SD), and when appropriate minimum and maximum values. Categorical variables will be summarized by frequencies and percentages. Where appropriate, 95% confidence intervals either around the sample means or mean differences will be furnished. All data collected will be presented in subject data listings.

Power Analysis

Post hoc power analysis was conducted using G*Power 3.1 (Faul, Lang, & Buchner, 2007) for this 2 x 7 mixed design (i.e., two treatment groups x 7 waves of measurements). Given the constraints on sample size ($n = 20$), a power analysis was conducted with the intent to detect the obtained power ($1 - \beta$) given: (1) level of significance (set at $\alpha = .05$), effect size (standardized F statistic varied at .15, .2, and .25) and (3) rate of autocorrelation (average correlations of repeated measures varied at .3, .5, and .7). Even though ascertaining what constitutes a small/medium/large effect size is, in part, context and discipline-dependent, using Cohen's (2008) taxonomy of small ($F = .10$) and medium ($F = .25$) we see below that sufficient power (.80) to obtain significance for the 2 x 7 first order interaction will be obtained for a medium effect size when the autocorrelation is .5 or higher and for a slightly smaller effect size ($F = .2$) when autocorrelation approximates .7. However if the effect size approximates .15 sufficient

power will not be obtained, regardless of magnitude of autocorrelation.

AutoCorr	Effect Size	Power
0.3	0.25	0.729
0.5	0.25	0.881
0.7	0.25	0.989
0.3	0.2	0.503
0.5	0.2	0.672
0.7	0.2	0.904
0.3	0.15	0.286
0.5	0.15	0.399
0.7	0.15	0.639

Cohen (1988). *Statistical power analysis for the behavioral sciences*. (2nd Ed.). Hillsdale, NJ: Lawrence Erlbaum.

Proposed Analysis

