For this 2 x 7 mixed design (i.e., two treatment groups x 7 waves of measurements) with a continuous level outcome, a two-way (completely within) repeated measures ANOVA will be performed with the overarching objective being the test of significance for the two-way treatment x time interaction (using $\alpha = .05$). If the two-way interaction is significant, simple effects analysis will be performed so as to assess at which time point significant differences for the treatment variable are obtained. Moreover, if the first order interaction is significant, trend analysis will be conducted in an effort to uncover any nonlinear patterns across time (up to polynomial $t - 1$, where $t = \text{time}$). Graphic displays will be provided so as to illuminate the nature of the findings and the between treatment trajectories.

All assumptions will be examined, including sphericity and homogeneity of variance/covariance matrices and any data anomalies (e.g., outliers) will be examined and treated accordingly. It should be kept in mind that given the small sample size ($n = 20$), there may still be substantive effects despite non-significant results, hence univariate and multivariate effect sizes will be reviewed (e.g., partial η^2).

There are many techniques beyond a mixed ANOVA approach that can more dynamically model the longitudinal nature of this design, such as multilevel modeling, generalized estimating equations, and/or latent growth curve modeling. However, those techniques will need to be deferred until a larger sample size is obtained. All analysis will be conducted using SPSS 21.0 or Stata 11.0.

Analysis Sets of ReCell Device Treatment vs. Control Comparison:

Safety Analysis Set:

The safety analysis population will include all enrolled subjects. Data will be analyzed based on treatment received. The number and percentage of subject who discontinued the study due to adverse event will be provided. Also, descriptive statistics, as

appropriate, will be provided for the following, by treatment:

- Delayed healing/non-healing of wound and donor site
- Graft loss
- Heterotopic ossification
- Infection
- Scar contracture
- Durability (i.e. abrasions/injuries at graft site due to graft fragility)
- Allergic response to trypsin
- Subject Complaint (pain and itching)
- Vital Signs
- Blood chemistries and hematology

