- Safety-related issues occurring through 24 weeks after treatment, other treatment-related adverse events requiring surgical intervention prior to 12 weeks post-treatment and all serious adverse event (SAE) occurrences.

For Adverse Events (AEs), a tabulation of incidence, number of subjects and percent of subjects experiencing AEs will be provided for:

- Serious AEs
- Severity
- Expected or Unexpected
- Relationship to Study Treatment
- Body System and preferred term

A listing of all AEs along with severity, relation to treatment, date and outcome will also be provided.

Effectiveness Analysis Set:

Preliminary and long-term effectiveness data will be summarized descriptively for each of the assessment intervals by presenting the number and proportion of treatment and donor sites that achieved healing. The treated wound site will be considered healed if 95% or greater re-epithelialization has occurred by Week 6 post-treatment. Donor sites (STSG 1:5, STSG 1:1.5 and ReCell) will be considered healed when $\geq 95\%$ of the donor site has re-epithelialized by Week 4 post treatment. Both Observer and Patient Assessment scales of the POSAS, and total POSAS scores will be summarized descriptively (mean, median, standard deviation, range) at Weeks 12 and 24. The Vancouver Scar Scale (VSS) assessment tool and total VSS scores will also be summarized descriptively (mean, median, standard deviation, range) at Weeks 12 and 24. Patient satisfaction and functional outcome ratings data will be summarized in terms of counts, percentages and other descriptive statistics.

Histology Analysis

Histological analyses will be performed on punch biopsies of ReCell-treated and control sites for Week 2, 4 and 12 and also of the pre-treatment biopsies taken from the INTEGRA™ MBWM treated wound site and adjacent normal skin. This biopsy of

normal skin serves as the control control for all other biopsies. At each assessment interval, histological parameters from both ReCell-treated and control biopsies will be compared to the same parameters as measured in normal skin. Data will be summarized descriptively.

Cell Suspension Preparation/Application Parameters Analysis

Data concerning biopsy size and thickness, wound size, and ReCell cell suspension application (e.g., volume and details for application) will be documented on the eCRF. Data will be summarized using descriptive statistics.

Demographic Data Analysis

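### Healing and the region-level binary safety outcomes are planned only as counts and percentages per treatment, so the planned tables show neither the within-subject difference nor its uncertainty

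*Combined protocol and SAP*

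**What the plan says.** Sections 2.3 and 5.1 describe a design in which one wound is split into two regions, treatment is randomised between them, and each subject is his or her own control. Section 5.1 states that "within-subject comparisons across a battery of measurements and evaluations will be made". On size, Section 5.7.2 says "A sample size of 20 subjects was selected based upon the amount of subject exposure considered necessary".

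Section 5.7.3 then sets out the outputs:

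- **Healing (Effectiveness Analysis Set):** summarised at each assessment interval by "presenting the number and proportion of treatment and donor sites that achieved healing".
- **Safety (Safety Analysis Set):** descriptive statistics that, as "appropriate, will be provided for the following, by treatment". The list includes delayed healing, graft loss, infection, scar contracture and durability.
- **Categorical variables in general:** counts and percentages.
- **Intervals:** "Where appropriate, 95% confidence intervals either around the sample means or mean differences will be furnished".
- **The one within-subject model (Proposed Analysis):** a repeated measures ANOVA, specified for a continuous outcome.

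Section 3 predicts non-inferiority without giving a margin. Specific Aim 2, for example, predicts that "more ReCell-treated areas will be healed to an extent defined as non-inferior compared to the control areas of the wound". Section 5.7.2 disclaims formal hypotheses and says the results may be used to refine a pivotal trial.

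**The concern.** The safety events are primary outcomes under Section 5.7.1, and healing is the main acute efficacy outcome. In a paired design, the evidence on a binary outcome lies in the subjects whose two regions differ: healed under ReCell only, or under control only. Two percentages side by side do not show how many such subjects there were. No interval is planned for a proportion or for a difference in proportions.

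Two things are at stake. First, the comparison that the design was built to make would not appear in the tables for these outcomes. A reader with only the tables could attach error to the difference only by treating the 20 ReCell and 20 control regions as independent. Second, planning a paired pivotal trial on a binary outcome requires the discordance rate, which marginal tables cannot supply.

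**Working it through.** **1. The plan's own figures.** The only power figures are for a "2 x 7 mixed design (i.e., two treatment groups x 7 waves of measurements") with n = 20. Using λ = f²·N·m/(1−ρ), with N = 20, m = 7 and df = 6 and 108, the case f = 0.25, ρ = 0.5 gives λ = 0.0625 × 20 × 7 / 0.5 = 17.5 and power 0.881, as stated. All nine cells reproduce within 0.001. They concern a continuous outcome, so they say nothing about healing or safety events. The plan states no figure for any binary outcome.

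**2. Marginals do not fix the paired evidence.** Write the paired table as a = both regions healed, b = ReCell only, c = control only, d = neither. With 18/20 healed under ReCell and 12/20 under control, a + b = 18 and a + c = 12. Both of the following satisfy these totals:

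| a, b, c, d | Difference | Newcombe 95%, unpaired | Newcombe 95%, paired |
|---|---|---|---|
| 12, 6, 0, 2 | 0.30 | 0.03 to 0.53 | 0.06 to 0.51 |
| 10, 8, 2, 0 | 0.30 | 0.03 to 0.53 | −0.01 to 0.54 |

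With 18/20 in both regions, 0, 2 or 4 discordant subjects are possible. The paired half-widths are then 0.157, 0.202 and 0.221, against 0.214 unpaired. Ignoring the pairing can therefore mislead in either direction.

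**3. Size in large-sample form.** With equal proportions p and within-subject correlation ρ, the Wald half-width is 1.96·√(2p(1−p)/n) unpaired. The paired value is that times √(1−ρ). At p = 0.90 and n = 20, the unpaired value is 1.96 × √0.009 = 0.186. At ρ = 0.5 the paired value is 0.186 × 0.707 = 0.131. The ratio is 0.84, 0.71 and 0.55 at ρ = 0.3, 0.5 and 0.7. It is 1 at ρ = 0, and 1.05 at ρ = −0.1, where the paired interval is slightly wider.

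**4. Size by exact enumeration.** The document inputs are 20 pairs and 95% intervals. The assumptions are equal true healing p in both regions, ρ of 0.3, 0.5 or 0.7, and a 20-point margin. The documents give neither a ρ for binary outcomes nor a margin.

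Cell probabilities are p11 = p² + ρp(1−p), p10 = p01 = p − p11, and p00 = 1 − p11 − 2·p10. At p = 0.8 and ρ = 0.5 these are 0.72, 0.08, 0.08 and 0.12.

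Each possible table receives Newcombe's interval, whose lower limit is D − √[(p1−l1)² − 2φ(p1−l1)(u2−p2) + (u2−p2)²]. D is the observed difference, and l and u are Wilson limits. φ = 0 for the unpaired form. For the paired form φ carries the continuity correction: its numerator is ad − bc, reduced by n/2 when it exceeds n/2 and set to 0 when it lies between 0 and n/2.

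Probability that the lower limit lies above −0.20:

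| True healing | ρ = 0.3, paired vs unpaired | ρ = 0.5 | ρ = 0.7 |
|---|---|---|---|
| 80% | 42% vs 34% | 50% vs 31% | 63% vs 27% |
| 90% | 52% vs 48% | 58% vs 48% | 68% vs 47% |
| 95% | 65% vs 63% | 70% vs 66% | 79% vs 69% |

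The unpaired figure at 80% falls as ρ rises because the observed differences then cluster near zero. An unpaired interval for 16/20 against 16/20 has half-width 0.247 and cannot exclude −0.20.

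Without the continuity correction of φ, the paired figures at 80% would be 47%, 58% and 73%, so the gain depends partly on the interval chosen. If all 20 subjects heal in both regions, both forms give ±0.161.

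**The case against.** A reader might infer more: that the plan discards the pairing and judges non-inferiority with needlessly wide uncertainty. The documents do not support this. No unpaired interval, no test of proportions and no margin is planned, so nothing planned is too wide; for these differences no uncertainty is specified at all. The pairing is not lost from the data either. Section 5.7.3 promises listings of all data by subject, and with 20 subjects the discordant pairs can be counted from them.

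Three further points carry weight:

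- Section 4.3 expects all regions to heal adequately, and Section 6.2 puts total graft loss and limb-affecting contracture at 5% to under 10%, and wound infection at 1% to under 5%. The precision gain is small at such rates unless the correlation is high.
- Planned intervals for mean differences, in an own-control design, can fairly be read as within-subject for the scar scales.
- Appendix H is listed as including a statistical management plan. It is not in the text available here and may hold table-level detail.

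These points limit the size of the concern but do not remove it. A listing is not a planned summary, and a comparison counted from it would be post hoc. Healing is reported at every assessment interval, including early visits when not all regions need have healed, and Section 6.2 puts partial graft loss at 10% or more. The descriptive aim is no obstacle, because a four-cell table is descriptive.

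**Conclusion.** The point holds as a gap in the planned summaries. For healing and the region-level binary safety outcomes, the tables specified in Section 5.7.3 do not deliver the within-subject comparison promised in Sections 2.3 and 5.1. The discordance rate that would inform a pivotal design can be found only by counting through listings.

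Under the stated assumptions, using a paired interval raises the chance of excluding a 20-point deficit by about 8 to 36 points at 80% healing, 4 to 21 at 90% and 2 to 10 at 95%. These gains require positive correlation between regions of the same wound, which is plausible but not documented, and some failures. There is no gain at zero correlation or if every region heals. The loss of discordance information from the tables does not depend on the assumed correlation or margin. No planned conclusion is invalidated.

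**What to change.** Amend Section 5.7.3 as follows:

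- For each binary outcome recorded separately for the two regions (healing at the 95% threshold, delayed healing, graft loss, infection, contracture, durability event) and at each visit, report the paired 2 × 2 table: both regions, ReCell only, control only, neither.
- Add the within-subject difference in proportions with a 95% paired score-type interval. Name the method in advance: Newcombe paired, stating whether φ is continuity-corrected, or Tango.
- Extend the sentence on confidence intervals to cover paired differences in proportions. For POSAS and VSS at Weeks 12 and 24, state that the interval is for the within-subject mean difference.
- Label all of this descriptive and add no hypothesis test.

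The cost is SAP wording and extra tables from data already collected. No additional subjects, visits or measurements are needed.

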2.3 Methodology /Technical Approach

In the proposed study, each patient will serve as his/her own control. Due to the nature of the study, only patients whose wounds have been previously successfully treated with INTEGRA™ MBWM as part of their standard of care will qualify for participation.

Therefore, as part of enrollment eligibility criteria for this study, the identified study wound will first be treated with INTEGRA™ MBWM. The wound will then be allowed to heal for approximately two to four weeks, at which time a viable granulation layer will have developed thus allowing for next stage STSG grafting. The timing of the STSG application will be determined by clinician judgment based on the state of the granulation process, which varies between patients, but typically takes 2 to 4 weeks.

Approximately two to four weeks after INTEGRA™ MBWM treatment, the studied wound will be divided into a ReCell-treated area (over 1:5 meshed STSG) and a control area treated with 1:1.5 meshed STSG (no ReCell). In all cases, the ReCell region may be up to 320cm² in size; the upper limit of application area for one ReCell kit, with a similarly sized control region. If the wound is larger than the combined ReCell and control regions (over 640cm²), the areas outside the study regions will be designated as non-study areas and treated according to standard of care. The same primary and secondary dressings will be used on ReCell-treated areas, control areas and donor sites. Once the study and control wounds are determined to have healed, standard local clinical practice will be followed.

Within-subject comparisons of the ReCell region and control region, in order to evaluate improvements associated with use of ReCell, a battery of measurements and evaluations will be made. These measurements are divided into three categories: safety and tolerability, preliminary effectiveness (acute healing process) and long-term effectiveness.

The safety of research participants is foremost. Therefore, efforts will be made to control risks to participants throughout the duration of their study participation. Wound healing time, donor site morbidity and histology will be assessed during an acute 6

week phase, with follow-up visits at Weeks 1, 2, 3, 4 and 6 post-treatment.

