- **Concomitant Medication Use:** Concomitant medication use (excluding anesthetic regimen) and all treatment regimens applied in the management of infection during the acute healing phase will be recorded in the eCRF. Concomitant medication used for the treatment of an adverse event occurring from time of receiving investigational product through Week 24 post-treatment will also be recorded in the eCRF.

In additional to above assessments, additional “visit specific” assessments will be made as outlined below:

At Week 1 post–treatment:

- **Bloodwork:** A blood sample (15 mls) will be drawn for hematological analysis including a complete blood count (CBC) with differential panel, coagulation studies to include prothrombin time (PT) and international normalized ratio (INR) and comprehensive metabolic panel (CMP), which is consistent with standard of care practices. The sample will be labeled and processed by WRNMMC laboratory medicine per institutional policy. Due to the nature of complexity and multi- system involvement resulting from trauma in the targeted subject population, the occurrence of a deviation from the institutional normal reference range(s) for laboratory assay results is anticipated. Therefore, laboratory levels falling outside of the “normal” reference range and/or with a change in test result of 20% from baseline value will be evaluated for clinical significance by the Principal Investigator and/or AI physician. Any laboratory value deemed clinically significant will be captured on the adverse event eCRF. Additional laboratory testing will be performed only as clinically indicated.

At Week 2, 4 and 12 post-treatment:

- **Histology: 3-mm** punch biopsies will be obtained by a physician investigator. A sample collection of 3mm diameter will be taken from both the control and ReCell treated sites and documented in the eCRF. Biopsies will be obtained from a centralized region of each wound. Biopsies will be taken for histologic analysis and analyzed to determine skin composition relative to normal skin.

At Week 12 and 24 post-treatment:

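### The histology analysis specifies only a comparison of each region with normal skin; the within-subject ReCell-versus-control comparison that Aims 2 and 3 call for is not written into it

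*Combined protocol and SAP*

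**What the plan says.** Section 3 sets the contrast. Aim 2 evaluates ReCell in "wounds treated with STSG over INTEGRA™ MBWM compared to a control site". Aim 3 evaluates "ReCell treatment of full-thickness wounds treated with INTEGRA™ MBWM compared to a control site". Histology is a listed evaluation under both, and Section 5.7.1 lists it as both a preliminary and a long-term efficacy endpoint.

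The histology text sets another contrast. The Histology Analysis paragraph in Section 5.7.3 states that, at every visit with biopsies, the parameters from the two regions "will be compared to the same parameters as measured in normal skin". It adds that the biopsy of "normal skin serves as the control control for all other biopsies", and that the data will be summarized descriptively. Section 5.5.4 gives the same purpose for the Week 2, 4 and 12 biopsies: "Biopsies will be taken for histologic analysis and analyzed to determine skin composition relative to normal skin".

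The general text points back to the aims. Section 2.3 refers to "Within-subject comparisons of the ReCell region and control region" as the basis for a battery of measurements, and Section 5.1 repeats the promise. Section 5.7.3 allows 95% confidence intervals around means or mean differences where appropriate, and promises subject listings of all data.

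**The concern.** The aims ask how ReCell over 1:5 mesh compares with 1:1.5 mesh alone in the same wound. The histology paragraph asks how far each region is from normal skin. These are different questions. The histological methods text in Section 5.5.4 expects the neodermis to start out thicker than normal dermis and to mature over months. Both regions may therefore differ from normal skin at the early biopsies whether or not ReCell has any effect. Two region-versus-normal summaries placed side by side describe maturation in each region. They do not report the treatment difference or its uncertainty.

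What is at stake is modest but real. Subjects undergo punch biopsies in both regions at three post-treatment visits. Section 5.7.2 says the results may be used to refine the design of a pivotal trial, and for that purpose the useful histology result is the paired difference and its standard deviation.

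**Working it through.** **The plan's own figures.** No figure is given for histology. The only figures in Section 5.7.3 are the nine power values for the 2 x 7 treatment-by-time interaction. They reproduce with noncentrality f² × N × m / (1 − ρ), N = 20, m = 7, on 6 and 108 degrees of freedom. For example, f = .25 and ρ = .5 give 0.0625 × 20 × 7 / 0.5 = 17.5 and power 0.881, as stated. All nine agree within 0.001. They have no bearing on histology, which has three post-treatment time points and not seven. The one explicit paired model in the plan therefore does not fit histology as written.

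**The contrasts side by side.**

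| Place | Contrast for histology |
|---|---|
| Section 3, Aims 2 and 3 | ReCell against control site |
| Sections 2.3 and 5.1 | ReCell region against control region, within subject (general; histology not named) |
| Section 5.5.4 | each sample against normal skin |
| Section 5.7.3, Histology Analysis | each region against normal skin |

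**What can be recovered.** Within a subject both regions share one normal-skin biopsy. For a quantitative parameter, (ReCell − normal) − (control − normal) = ReCell − control, so the mean difference follows from the two planned summaries. Its standard error does not, because that needs the covariance between regions, which separate summaries do not show. It can be calculated from the subject-level data.

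**Size, for illustration.** Inputs: n = 20 (Section 5.7.2), all pairs complete (assumed), a continuous parameter with the same SD in both regions (assumed), between-region correlation r (assumed; Section 5.7.3 uses .3 to .7 for repeated measures, extended here to .8).

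SE of the difference = SD × √(2(1 − r)/20)

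- Read as unpaired (r = 0): √(2/20) = 0.316 SD
- r = .3: √(1.4/20) = 0.265 SD
- r = .5: √(1.0/20) = 0.224 SD
- r = .7: √(0.6/20) = 0.173 SD
- r = .8: √(0.4/20) = 0.141 SD

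Paired 95% confidence interval half-widths (t on 19 degrees of freedom) are 0.55, 0.47 and 0.36 SD at r = .3, .5 and .7. With the regions treated as independent (38 degrees of freedom) the half-width is 0.64 SD.

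**The case against.** The strongest reply is that the comparison is already covered. Sections 2.3 and 5.1 promise within-subject comparisons across the measurements, Section 5.7.3 allows mean differences with confidence intervals, and its analysis sets stand under a heading that names ReCell against control. Normal skin is also a sensible reference for the stated purpose of judging the normality of new tissue. The predictions attached to Aims 2 and 3 concern healing, scar and functional outcomes, and satisfaction, not histology. Appendix H is listed as containing a statistical management plan, and its content was not available to check.

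Much of this stands, and it rules out several stronger readings that a reader might infer:

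- *That the comparison will not be made.* The documents support only that it is not specified for histology.
- *That the pairing is wasted, or that histology cannot answer the aims.* The paired samples are collected and the common reference cancels for quantitative parameters.
- *That the plan would mistake one significant and one non-significant result for a treatment effect.* No histology tests are planned. If someone did read the two comparisons by significance, a simulation gives discordant results in 5% to 34% of trials. It assumes no true ReCell-control difference, both regions 0.3 to 0.7 SD from normal, correlations .3 to .7 and n = 20. That is a caution for interpretation, not an error rate of this plan.

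The reply does not close the gap. The general provisions name no histology parameter or paired summary, and the one paragraph specific to histology names another comparator. An analyst would reasonably follow the specific paragraph.

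**Conclusion.** The point holds as a gap in specification. The written histology method does not estimate the contrast in Aims 2 and 3, although the design supplies the paired data to do so. The precision figures (0.26 to 0.14 SD paired, against 0.32 SD unpaired) are illustrative. They depend on an assumed correlation, 20 complete pairs and a continuous parameter. The documents define no histology score: Section 5.5.4 describes a written dermatopathology report, and of the features it mentions tissue thickness is the plainest continuous one. At the low end of the correlation range the gain in precision is small; the main reason to act is that the reported contrast should match the aim. The endpoint is secondary, the study is descriptive, and the primary safety outcomes are not affected. The change is worth making because it costs so little.

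**What to change.** In the Histology Analysis paragraph of Section 5.7.3:

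1. Name the histology parameters to be summarized, and whether each is quantitative (such as tissue thickness) or categorical (such as rete ridges present or absent).
2. Make the main summary at Weeks 2, 4 and 12 the within-subject ReCell-minus-control difference: mean, SD and paired 95% confidence interval for quantitative parameters. For categorical findings give paired counts (both regions, ReCell only, control only, neither). State the number of complete pairs each time.
3. Keep the comparison of each region with normal skin as a secondary, descriptive reference.

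The cost is a few sentences and one additional table from biopsies already planned. No extra visit, sample or test is needed. The named parameters do need to be recorded in the same way for both regions, so the list should be settled before the biopsies are read.
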